- Another randomized trial suggests that a live call the day prior to the procedure can increase the adequacy of the bowel prep.

PROJECT QUESTIONS AND HYPOTHESES

This project will address the following question:

Does an “enhanced” IVR-T protocol differ in effectiveness from the standard IVR-T protocol in reducing missed appointments and late cancellations for GI endoscopy?

Hypothesis 1: The enhanced IVR-T protocol will be more effective.

RESEARCH DESIGN AND METHODS

We will conduct a randomized trial over a 6-month period (March through September 2019) in the 3 GI endoscopy clinics (Franklin, Rock Creek, and Lone Tree). All members currently receive a text reminder 7 days prior to their procedure, which rolls over to a telephone reminder if the text cannot be delivered or the member’s phone is not text-enabled. Members will be randomized either to receive this standard IVR-T protocol or to receive an enhanced reminder protocol.

Inclusion criteria:

- a. Members scheduled for any GI procedure (upper endoscopy, colonoscopy, or both), with or without anesthesia, at all three clinical sites (Franklin, Rock Creek, Lone Tree) will be included if their procedure is scheduled \geq 2 days prior to the procedure. The IVR-T protocol will be adapted based on the wait time between appointment scheduling and the date of the procedure.
- b. Members with all clinical indications (screening, diagnosis, or surveillance), will be included.

Exclusion criteria:

- a. KPCO members who request not to participate in research or not to receive IVR-T or email outreach
- b. KPCO members in the “break the glass” or “code pink” protocols.
- c. Members whose procedure is scheduled $<$ 2 days prior to the procedure.

Randomization: Beginning in March 2019 (or on completion of all necessary design steps), we will use the randomization algorithm in the Structured Query Language program that manages the IVR relational database to assign each visit for a procedure at all three sites to one of the two interventions. Since members with multiple procedures on different days during the study period could receive different interventions for different visits, we will limit the statistical analysis to the first randomized appointment during the project period. Randomization will be stratified by clinic site.

Intervention content

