- a. **Standard reminder protocol (usual care):** Members randomized to this arm of the study will receive a single text message that “rolls over” to an IVR automated phone call if the text cannot be delivered. This message will be delivered 7 business days prior to

the appointment. This replicates the current protocol for GI procedures. Of note, members who schedule appointments within 7 days of the procedure currently receive no reminders.

- b. **Enhanced reminder protocol:** The enhanced reminder protocol will include multiple reminders, multiple reminder modalities, and motivational messages. The timing of reminders will depend on the wait time between the date the appointment is made and the date of the appointment, as shown in Table 2.

Table 2. Timing of reminders for intervention group

Wait time between date appointment made and date of visit	Email †	IVR-1	IVR-2	IVR – Prep (colon only)
≥ 15 calendar days	14 calendar days	7 business days	5 business days	1 calendar day
8-14 calendar days	6-12 calendar days	5 business days	3 business days	1 calendar day
7 calendar days	5 calendar days	5 business days	3 business days	1 calendar day
6 calendar days	4 calendar days	2-3 business days (2 days if appt on Monday)	1 business day	1 calendar day
5 calendar days	3 calendar days	1 business day	x	1 calendar day
4 calendar days	2 calendar days	1 business day	x	1 calendar day
3 calendar days	1 calendar day	0-1 business day (No IVR if appt on Monday)	x	1 calendar day
2	x	x	x	1 calendar day
0-1 days	x	x	x	X

- An email reminder will be sent to all members who have provided their personal email information according to the schedule in Table 2.
- For IVR-T reminders, the rationale for choosing business days (Monday through Friday) rather than calendar days is that the GI appointment desk is only open on business days to cancel or reschedule procedures.
- Members scheduled for colonoscopy will also receive a single IVR-T reminder to begin their bowel prep the morning of the calendar day prior to the procedure.
- Brief motivational messages will be added to email, text and telephone messages. These messages will be “generic” rather than tailored for the clinical indication or type of procedure.

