1. We will develop a multivariable logistic regression model to predict appointment loss using approaches similar to prior IVR-T interventions. Clinic site will be included as a fixed effect. We will include linear and quadratic terms for continuous predictors and include both terms in the final model if statistically significant. Missing values for each predictor will be included as a separate category. Backward selection with Wald chi-square tests will guide the selection of predictors. The final prediction model will include an indicator variable for treatment group and all covariates with *p*-values <0.05. The discrimination of the model will be assessed with the *c*-statistic. We will use this prediction rule to stratify participants into risk quartiles and will assess the effectiveness of the intervention in each quartile.
2. We will assess the effectiveness of the intervention in each of the 3 participating clinics, after adjusting for predictors of missed appointments/late cancellations, to provide preliminary information on site-level factors that may modify intervention effectiveness.
3. We will analyze the effectiveness of the intervention in the subgroup of individuals who schedule their endoscopies \leq 7 days prior to the procedure, since these individuals will receive no reminders under the standard protocol.

Human subjects

The standard reminder protocol includes a text message that “rolls over” to an IVR automated phone if the text cannot be delivered. The GI Clinic has received permission from the KPCO Compliance Office to send emails to the private email addresses of KPCO members.

Study Risks: This study utilizes current standard protocols for contacting KPCO members and data collected during the course of routine clinical care to improve efficiencies in the delivery and quality of care for patients. Therefore, the primary risk of this study is the potential for loss of confidentiality and privacy of a member, through a loss or inappropriate disclosure of study data. There are no known risks to investigators or staff.

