Appendix 1. Study Variables

Variable	Use, comments, questions
Age	*
Sex	*
Race/ethnicity (white, Asian, black, Latino, Native American, unknown/other)	*
Marital status	
Employment	
Comorbidities	Quan index *
Mental health diagnoses	From MHRN list
Substance use diagnoses	From MHRN list
Number of address changes in last 12 months	New variable – created for [name]’s project
Number of telephone contact # changes in last 12 months	New variable – created for [name]’s project
Number of insurance plan changes in last 12 months	New variable – used by [name]
Clinic site	*Franklin, Lone Tree, Rock Creek
Day of week of appointment	
Exact time of day of appointment	
Health insurance type	*
Duration of enrollment in KPCO	
New member in KPCO	Individuals enrolled < 12 months will be defined as “new enrollees.” May conduct separate subgroup analysis for these individuals. [name] notes that several “segments” of new members have been defined for onboarding interventions.
Appointment lead time	* Exclude if <10 days
Number and rate of ED visits in prior 12 months	*
Number and rate of hospitalizations in prior 12 months	*
Number and rate of missed primary care appointments in prior 12 months	* We will consider various way of analyzing prior missed appointments: a) one or more b) relative risk for each additional missed visit

Number and rate of missed specialty care appointments in prior 12 months	*
Number and rate of missed GI endoscopy appointments in prior 12 months	
Appointment outcome (missed, kept, cancelled)	*
Bowel prep adequacy	Boston Bowel Prep scale (0-9 scale from GI smart set)
Applied for or received medical-financial assistance in last year	New variable – any IHR experience with this? [name] has a contact in KPNW who has extracted this variable UCDA also says that this is accessible.
Unpaid account balance	New variable – how to define?
Geo-located residence	We will use census tract as the primary unit of analysis
Distance from residence to clinic	
Picked up prep kit from KP Pharmacy	Prep kits provided by prescription only; may be picked up from non-KP pharmacies.

Notes:

1. include missing as a category for each variable
2. *= significant variable in prior predictive model(s) in primary care
3. For members with <12 months of enrollment, we will assess utilization from the beginning of enrollment to the date of the first scheduled primary care appointment.

Refs:

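### Appendix 1's lead-time exclusion contradicts the 2-day entry rule and would empty subgroup 3, whose 7-day cut also needs a unit and a booking-day rule

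*Combined protocol and SAP*

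**What the plan says.** **Entry rule.** Under Research Design and Methods, the inclusion criteria say that members "will be included if their procedure is scheduled" 2 or more days ahead. The exclusion list repeats the rule as under 2 days.

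**Appendix 1.** The row for appointment lead time carries the note "Exclude if <10 days".

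**Standard arm.** Under Intervention content: "This message will be delivered 7 business days prior to" the appointment. The same paragraph adds that "members who schedule appointments within 7 days of the procedure currently receive no reminders". The background and the opening of the design section also put the current reminder at 7 days, without a unit.

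**Subgroup 3.** The third planned subgroup analysis in section 10 takes those who book at most "7 days prior to the procedure, since these individuals will receive no reminders under the standard protocol". No unit is given.

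**Table 2 (enhanced arm).** Members are grouped by wait in calendar days, but IVR-1 and IVR-2 are timed in business days, defined as Monday to Friday. The 7-day row reads, in the order wait, email, IVR-1, IVR-2, prep message: "7 calendar days 5 calendar days 5 business days 3 business days 1 calendar day". Two shorter rows have a Monday provision for IVR-1: the 3-day row, "0-1 business day (No IVR if appt on Monday)", and the 6-day row, "2-3 business days (2 days if appt on Monday)". The 7-day row has none.

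**The concern.** Subgroup 3 is the planned comparison of enhanced reminders with no reminder at all, so its membership should follow from who actually gets no standard message. Two statements put that at risk. The Appendix 1 note, if programmed as written, leaves the subgroup with nobody in it and gives an analysis set that the entry criteria do not describe. And a cut at 7 days does not match a message sent at 7 business days if the cut is counted in calendar days.

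The same mixing of units appears in Table 2. In the 7-day row the first automated message falls due on the day the member books, and the table does not say whether to send it. The 3-day row settles the same coincidence for Monday visits by dropping the message.

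**Working it through.** The plan gives no figure to reproduce here. The check is calendar counting, assuming procedures on Monday to Friday and ignoring public holidays.

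**Step 1. Business days converted to calendar days before the visit.**

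| Business days | Mon | Tue | Wed | Thu | Fri |
|---|---|---|---|---|---|
| 1 | 3 | 1 | 1 | 1 | 1 |
| 2 | 4 | 4 | 2 | 2 | 2 |
| 3 | 5 | 5 | 5 | 3 | 3 |
| 4 | 6 | 6 | 6 | 6 | 4 |
| 5 | 7 | 7 | 7 | 7 | 7 |
| 7 | 11 | 11 | 9 | 9 | 9 |

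**Step 2. Appendix 1 against the entry rule.** The entry rule keeps waits of 2 days or more; the note keeps waits of 10 or more. Subgroup 3 in calendar days is waits of 2 to 7, all below 10, so none survive. Every row of Table 2 from 2 to 7 days is removed as well, and so are the 8- and 9-day waits in the next row.

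**Step 3. Subgroup 3 under each reading of its 7 days.**

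- Cut and message both in business days: everyone without a standard reminder is already inside the cut.
- Both in calendar days: nobody is missed.
- Cut in calendar days, message at 7 business days: the message is due 9 calendar days before a Wednesday to Friday visit and 11 before a Monday or Tuesday visit. It is due before booking for waits up to 9 − 1 = 8 and 11 − 1 = 10 days respectively. Members above 7 days and within those limits get no standard reminder but are left out.

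When cut and message share a unit, a member who books exactly at the cut has a message due that day. The plan's statement that this member gets none then implies that booking-day messages are not sent. The plan never says so directly.

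On the mixed reading, with weekday bookings, the booking/visit weekday combinations are:

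- waits of 2 to 7 days: Mon 5, Tue 4, Wed 4, Thu 4, Fri 4, total 21;
- wait over 7 days, message due before booking: 10 days (Mon) and 8 days (Tue, Wed, Thu, Fri), total 5;
- message due on the booking date: 11 days (Mon, Tue) and 9 days (Wed, Thu, Fri), total 5.

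These are calendar combinations and say nothing about numbers of members. As an illustration only, an even spread of bookings would add 5/21 = 24%, or 10/21 = 48% if booking-day messages are not sent. Weighting by 1/wait gives 12% or 21%; weighting by wait gives 42% or 90%. The spread shows that the gain is not estimable from the documents.

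**Step 4. Table 2, 7-day row.** Margin = wait − calendar lag of IVR-1 = 7 − 7 = 0 on all five visit weekdays. A public holiday in the interval would push the due date before booking. The only other zero is a 3-day wait for a Monday visit (3 − 3), which the table suppresses. Every other row with an IVR-1 has a margin of at least 1 day.

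**Step 5. Primary comparison.** Assume that 2% to 5% of enhanced-arm members fall in the 7-day row, and that losing IVR-1 costs 0.9 to 1.4 percentage points (the gains from a second reminder in the sponsor's primary care trial, quoted in the background). The shift is then 0.02 × 0.9 = 0.02 to 0.05 × 1.4 = 0.07 points.

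**The case against.** **The appendix note looks like a leftover.** It sits in a column of comments and queries, and note 3 of the same appendix refers to a primary care appointment. The body states the 2-day rule twice, and Table 2 schedules messages for short waits. It is therefore clear which rule should govern. But Appendix 1 is the list from which variables will be programmed, and the note is worded as an instruction.

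**One shared unit is the natural reading of the 7 days.** The sentence about members who get no reminder follows closely on the 7-business-day statement. This stands to the extent that the gap exists only on the mixed reading. That reading is still not contrived: it uses the only units the plan states, calendar days for waits and business days for the message.

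**The harm in Table 2 is not shown.** Nothing in the documents says that a message on the booking day is ineffective. The member also gets IVR-2, an email if an address is on file and, for colonoscopy, a prep message. Moving IVR-1 to 4 business days gains only one day for Monday to Thursday visits, a gap the table already accepts for 8-day waits. All of this stands, so the row is a minor point.

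**The subgroup is imprecise either way.** Assume that subgroup 3 is 10% of 13,000, or 650 per arm. The difference detectable with 80% power is 2.8 × √(2 × 0.068 × 0.932 / 650) = 3.9 points. It falls to 3.5 with 24% more members and 3.2 with 48% more, against a planned overall effect of 1.4 points (6.8% vs 5.4%). This too stands.

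A reader might infer that subgroup 3 is biased. The documents do not support that: lead time and visit weekday are fixed at booking, so the arms stay comparable inside any cut based on them.

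**Conclusion.** The point holds in three parts of unequal weight.

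1. The Appendix 1 note contradicts the entry rule. Applied literally, it empties subgroup 3 and Table 2's 2- to 7-day rows. This needs no assumption about units, visit days or waits beyond reading subgroup 3 as 2 to 7 calendar days.
2. On the mixed-unit reading, subgroup 3 omits some members waiting 8 to 10 days who also get no standard reminder. The cost is precision, and its size is unknown without a wait distribution.
3. For weekday procedures, the 7-day row makes IVR-1 due on the booking date and gives no rule for it. The documents do not state procedure days. Five business days before a Saturday visit is 5 calendar days, and there the problem would not arise.

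A reader might go further and infer that subgroup 3 is too narrow on any reading, or that its proper limits are always 9 and 11 days. Neither follows. There is no gap when cut and message share a unit, and the longer limits apply only if messages due on the booking date are not sent. Nor is there ground for inferring that the primary result is compromised. With the 2-day rule governing the analysis set, the effect there is negligible, at 0.02 to 0.07 points under the assumptions shown.

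**What to change.** - **Appendix 1:** change the lead-time note to exclude waits under 2 days, in line with the entry criteria.
- **Subgroup 3:** define it as members to whom no standard message is sent, given lead time and visit weekday, and state the unit. State also whether a message due on the booking date is sent. With a message at 7 business days and weekday visits, the subgroup is waits of 2 to 8 calendar days for Wednesday to Friday visits and 2 to 10 for Monday and Tuesday visits. The limits become 9 and 11 only if booking-day messages are not sent.
- **Table 2, 7-day row:** mark IVR-1 as not sent, as the 3-day row does for Monday visits, or set it to 4 business days or fewer. At 4 business days it falls 4 to 6 calendar days before the visit, always after booking. Moving IVR-2 to 2 business days would keep the present spacing.

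The cost is one appendix note, one or two sentences and one table row, best settled before the reminder program and analysis code are written. No extra participants, staff or data are needed: lead time and day of week of the appointment are already listed in Appendix 1.

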- For the duration of this intervention, the GI clinic will discontinue all live pre-procedure reminders so that we can assess the effectiveness of a purely automated intervention. Staff will continue post-procedure calls to assess service quality. Selective live reminders for members at high risk of missed appointments will be assessed in Step 3 of this project.

Intervention delivery: All interventions by email, text and telephone will be delivered by secure messages from the Automated Communication Technology (ACT) team in the KPCO

Institute for Health Research. At present, GI clinic nurses or staff make live reminder calls to some members as time allows; these calls will be stopped for the duration of the Step 1 trial.

Over the 6-month period of the project, we estimate that approximately 2300 visits per month will be scheduled across the 3 participating sites. After anticipated exclusions (10% of total cases), we estimate that there will be approximately 2100 eligible appointments per month. We project that the study will run from March 8, 2019 through September 7, 2019 to achieve the proposed sample size of approximately 13,000 appointments. The duration of the study will be dictated by the number of appointments necessary to detect an operationally significant reduction in the rate of appointment loss, as described in the sample size calculations below. We will monitor recruitment during the study and adjust the duration of the randomization period as necessary to achieve the projected sample size.

9. Study Measures

Outcome variable: The primary outcome for the study will be “appointment loss”, defined by GI leaders as the combined rate of prior day cancellations, same-day cancellations, and missed clinic appointments (“no shows”). The rationale for this outcome definition is that it is difficult to schedule new procedures within this time frame. As a secondary outcome, we will assess the adequacy of the bowel preparation for colonoscopy only.

Covariates: To describe the project participants and identify clinically and operationally relevant subgroups, we will measure patient covariates that we have used in prior IVR-T evaluations in primary care clinics, as well as variables specific to the GI clinic setting. These variables are listed in Appendix 1. All variables will be drawn from the IHR Virtual Data Warehouse (VDW), KPCO appointment scheduling system, or endoscopy data from Clarity.

10. Sample size and statistical analysis

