Sample size calculation: As shown in Table 1, “appointment loss” in the 3 GI clinics has been 6.8% from January – mid-October 2018. Across sites, approximately 2580 procedures/month were scheduled, and 175 were missed. Using standard parameters for Type 1 error (0.05, two-sided) and Type 2 error (0.20), the necessary sample to detect differences between standard and enhanced IVR-T protocols is:

Table 3. Sample Size Estimates

Detectable difference in appointment loss	N total (per group)	Duration of project (months)
3% absolute difference (6.8% vs. 3.8%)	2654 (1327)	1.3
2% absolute difference (6.8% vs. 4.8%)	5644 (2822)	2.7
1% absolute difference (6.8% vs. 5.8%)	21244 (10622)	10.1
20% relative difference*	11112 (5556)	5.3

(6.8% vs. 5.4%)		
-----------------	--	--

*Effect consistent with prior KPCO trials and systematic reviews of missed appointment interventions

Based on these calculations, a 6-month study will provide statistical power to detect a 20% relative difference in appointment loss.

Analytic plan Statistical analyses will be consistent with approaches used in prior IVR-T interventions. Patient demographic and clinical characteristics will be compared between the 2 groups using *t*-tests for normally distributed continuous variables, Wilcoxon rank tests for non-normally distributed continuous variables, and chi-square tests for discrete variables. We will assess the effectiveness of the intervention across the 3 participating clinics, after adjusting for predictors of missed appointments/late cancellations. To estimate the number of additional kept visits and available appointments per week that would result if the most effective intervention were implemented for all visits that met inclusion criteria, we will multiply the average number of visits at each clinic by the sum of the rate reduction in missed appointments and the rate increase in cancelled appointments at that clinic.

We will conduct three planned subgroup analyses:

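### The plan compares only the sum of no-shows and late cancellations between arms, and its listed outcome field lacks the cancellation timing needed to build that sum or show which part changed

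*Combined protocol and SAP*

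**What the plan says.** Under Project Questions and Hypotheses, the trial asks whether the enhanced protocol differs from the standard one "in reducing missed appointments and late cancellations for GI endoscopy". That question names two targets.

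Section 9 (Study Measures) defines the primary outcome, appointment loss, as "the combined rate of prior day cancellations, same-day cancellations, and missed clinic appointments". It gives a reason: "The rationale for this outcome definition is that it is difficult to schedule new procedures within this time frame". It then adds one further outcome: "As a secondary outcome, we will assess the adequacy of the bowel preparation for colonoscopy only". The prediction model and risk-quartile analysis in section 10 also concern appointment loss.

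Missed and cancelled rates appear separately in one place. In section 10 (Analytic plan), the projected weekly gain in kept visits and open slots is the average number of visits at a clinic multiplied by "the sum of the rate reduction in missed appointments and the rate increase in cancelled appointments at that clinic". The timing of those cancellations is not given, and no test or interval is attached.

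Appendix 1 lists the outcome field as "Appointment outcome (missed, kept, cancelled". It has three levels and no cancellation date. Table 1 shows that the clinics already report no-shows, same-day cancellations and prior-day cancellations separately.

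**The concern.** A reminder can make a member attend, or make a member who would not have come cancel instead. If that cancellation falls on the day before or the day of the procedure, it stays inside the composite. Table 2 makes this possible. The column "IVR – Prep (colon only" places a message to enhanced-arm colonoscopy members on the calendar day before the procedure, and some short-wait members get another reminder one business day before. The plan itself allows for cancellations to rise, since its operational formula includes such a rise.

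The trial could therefore end with a small or null composite difference and no prespecified way to say whether no-shows fell, late cancellations rose, or neither moved. A favourable composite would likewise not show which kind of loss improved. Operational leaders could also receive two results that disagree, because section 9 treats late cancellations as loss while the section 10 formula credits cancellations without distinction. Components chosen after the data are seen would carry less weight than components named now.

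**Working it through.** **Inputs.** Table 1 (2018): Franklin no-show 2.5%, same-day 2.6%, prior-day 4.1%, N 7,612; Rock Creek 1.2%, 1.2%, 2.4%, N 7,592; Lone Tree 1.2%, 1.0%, 3.2%, N 9,283. Section 10: composite control rate 6.8%, "Type 1 error (0.05, two-sided) and Type 2 error (0.20"). Section 8 text on enrolment: about 13,000 appointments, so about 6,500 per arm. The size of any fall in no-shows, and the share that becomes prior-day cancellation, are not in the documents. Both are assumptions and are shown over a range.

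**The plan's own figures.** The 6.8% reproduces: 175/2,580 = 6.78%, and the stated site totals weight to (700.3 + 364.4 + 603.4)/24,487 = 6.81%. The 5,556 per group in Table 3 does not reproduce from the printed 6.8% vs. 5.4%. The usual pooled formula gives 4,587, and 5,556 corresponds to 6.8% vs. 8.2%. The printed number is larger than needed, and nothing below depends on it.

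**Component rates, weighted by N.**
- No-show: (190.3 + 91.1 + 111.4)/24,487 = 1.60%
- Same-day: (197.9 + 91.1 + 92.8)/24,487 = 1.56%
- Prior-day: (312.1 + 182.2 + 297.1)/24,487 = 3.23%

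These sum to 6.40%, not 6.81%, because the Lone Tree components sum to 1.2 + 1.0 + 3.2 = 5.4% against a stated 6.5%. No-shows are 1.60/6.8 = 24% of the composite.

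**Power.** Power = Φ[(d − 1.96·SE0)/SE1], with SE0 = √(2p̄(1−p̄)/n), SE1 = √([p1(1−p1) + p2(1−p2)]/n) and n = 6,500. It counts significance in the direction of benefit only, so under no effect it is 2.5%.

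For a 40% relative fall in no-shows (0.64 points):
- No-show alone, 1.604% to 0.962%: (0.00642 − 1.96 × 0.00197)/0.00197 = 1.29, power 90%.
- Composite with no offset, 6.80% to 6.16%: (0.00642 − 1.96 × 0.00432)/0.00432 = −0.47, power 32%.
- Composite with half of the fall becoming prior-day cancellation, 6.80% to 6.48%: (0.00321 − 1.96 × 0.00437)/0.00437 = −1.23, power 11%.

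| Relative fall in no-shows | No-show power | Composite, no offset | Half offset | Three-quarters offset |
|---|---|---|---|---|
| 20% (0.32 points) | 33.5% | 11% | 5.5% | 3.8% |
| 30% (0.48 points) | 66% | 20% | 7.9% | 4.6% |
| 40% (0.64 points) | 90% | 32% | 11% | 5.5% |
| 50% (0.80 points) | 99% | 46% | 15% | 6.6% |

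In the 40% row, dilution costs 90 − 32 = 58 points and a half offset costs a further 32 − 11 = 21.

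**Sensitivity.** At 5,556 per arm the 40% row begins 85%, 28%, 10%. Starting the composite at 6.40% gives 33% and 11% in place of 32% and 11%. If the missing 1.1 points at Lone Tree were all no-shows, the no-show baseline would be 2.02% and power for a 40% fall 96%.

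**Sections 9 and 10 side by side.** Suppose no-shows fall 0.6 points and prior-day cancellations rise 0.6. The composite changes by −0.6 + 0.6 = 0. The section 10 formula, read as written, gives 0.6 + 0.6 = 1.2 points, or 0.012 × 2,580 = 31 slots per month across the sites.

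**The case against.** The composite is deliberate. GI leaders defined it, its reason is stated, and each unfilled slot is costed at about $1,200 whatever the cause. On that view a no-show that turns into a prior-day cancellation is still a lost slot, and an unchanged composite is the right answer. This stands.

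A reader might infer that only the composite is analysed. The documents do not support that, since the section 10 estimate needs separate missed and cancelled rates. That estimate is descriptive, however, and does not time the cancellations. A reader might also infer that Appendix 1 cannot isolate no-shows. It can, because missed and cancelled are separate levels. What it cannot separate is prior-day, same-day and earlier cancellation. Appendix 1 is a working list and the scheduling system is a named data source, so the gap is one of specification rather than of available data.

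The offset mechanism is also limited. The day-before message is described as a prompt to start bowel preparation. For a Monday procedure it falls on a Sunday, when the appointment desk is closed. For waits of 7 days or more, the other automated calls and texts come 3 to 7 business days ahead, so the cancellations they prompt can fall outside the loss window, a shift the composite does register. Finally, a 40% fall is twice the 20% relative effect that the plan projects for the composite. At 20%, a no-show comparison would usually be inconclusive. This argues against giving no-show confirmatory status, not against reporting it.

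**Conclusion.** The point holds as a gap in specification and interpretation. The plan asks about two things, compares their sum, and lists an outcome field from which that sum cannot be built without adding cancellation timing. Its operational formula can also credit cancellations that the primary outcome counts as losses: 1.2 points against zero in the worked example.

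It would be tempting to conclude that the primary test is biased, or that opposing movements are the main reason a no-show benefit would go unseen. Neither follows. The test answers the lost-slot question correctly, and 58 of the 79 points of power lost in the 40% illustration come from no-shows being about a quarter of the composite. The power figures rest on assumed effect sizes and offset shares, on about 6,500 analysed appointments per arm, and on Table 1 rates whose Lone Tree components do not add up to the stated total. The case for the change does not depend on any one of those values.

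**What to change.** Keep the primary outcome and sample size. Then:

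1. Prespecify no-show, same-day cancellation and prior-day cancellation as secondary outcomes, each as a difference in proportions between arms with a 95% confidence interval, among first randomized appointments. Near the Table 1 rates, the half-width 1.96·√(2p(1−p)/6,500) is about 0.43 points for no-show, 0.43 for same-day and 0.61 for prior-day cancellation.
2. Recode the Appendix 1 outcome as kept, no-show, same-day cancel, prior-day cancel and earlier cancel, derived from scheduling timestamps, and define the primary outcome from those levels.
3. In the section 10 formula, count only the increase in cancellations outside the appointment-loss window. In the worked example this lowers the result from 1.2 to 0.6 points, not to zero, because the fall in missed appointments still enters in full. The estimate should therefore be printed beside the change in appointment loss.
4. Reconcile the Lone Tree components with their total in Table 1.

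The cost is a few lines of analysis plan and one derived field. The downside is three extra estimates, to be presented as estimation without confirmatory claims. Ranking no-show as a key secondary outcome is optional, given its power of about a third for a 20% fall.
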